3.1.5. Serologically Evaluable Full Analysis Set for HBsAg Loss/Seroconversion

The Serologically Evaluable Full Analysis Set for HBsAg loss/seroconversion includes all subjects who were randomized and had received at least 1 dose of study drug, and with HBsAg positive and HBsAb negative or missing at baseline. Subjects will be analyzed according to the treatment they were randomized to during the double-blinded phase.

3.1.6. DXA Analysis Set

DXA scans will be performed only at sites in China with capability.

3.1.6.1. Hip DXA Analysis Set

The Hip DXA Analysis Set includes all subjects who were randomized and had received at least 1 dose of study drug, and had nonmissing baseline hip BMD values. Subjects will be analyzed according to the treatment they actually received during the double-blinded phase.

3.1.6.2. Spine DXA Analysis Set

The Spine DXA Analysis Set will include all subjects who were randomized and had received at least 1 dose of study drug, and had nonmissing baseline spine BMD values. Subjects will be analyzed according to the treatment they actually received during the double-blinded phase.

3.2. Subject Grouping

For efficacy analysis using FAS and Serologically Evaluable Full Analysis Set, subjects will be analyzed by randomized treatment during the double-blinded phase. For efficacy analysis based on the PP analysis set and safety analysis, subjects will be analyzed by actual treatment received during the double-blinded phase. The actual treatment received will differ from the randomized treatment only when their actual treatment differs from randomized treatment for the entire double-blinded treatment duration.

3.3. Strata and Covariates

Randomization was stratified by plasma HBV DNA level ($< 7 \log_{10}$ IU/mL, $\geq 7 \log_{10}$ IU/mL - $< 8 \log_{10}$ IU/mL, $\geq 8 \log_{10}$ IU/mL) and oral antiviral treatment status (treatment-naïve vs treatment-experienced) at screening. HBV DNA strata will be reclassified using baseline HBV DNA level for stratified statistical analysis.

3.4. Examination of Subject Subgroups

The primary endpoint will be analyzed for the following subject subgroups:

- Age: (a) < 50 years and (b) ≥ 50 years
- Sex: (a) male and (b) female
- Baseline HBV DNA: (a) $< 7 \log_{10}$ IU/mL and (b) $\geq 7 \log_{10}$ IU/mL
- Oral antiviral treatment status: (a) treatment-naïve and (b) treatment-experienced
- Study drug adherence: (a) $< 95\%$ and (b) $\geq 95\%$ (based on adherence up to Week 48 Visit)
- Genotype: (a) B, (b) C, and (c) Other
- Baseline ALT by central laboratory normal range: (a) \leq ULN and (b) $>$ ULN
- Baseline fibrotest score: (a) < 0.75 and (b) ≥ 0.75

3.5. Missing Data and Outliers

3.5.1. Missing Data

A missing datum for a given study analysis window may be due to any of the following reasons:

- A visit occurring in the window but data were not collected or were unusable
- A visit not occurring in the window
- A subject permanently discontinuing from the study before reaching the window

For the primary endpoint and the secondary efficacy endpoints involving proportions, missing data will be handled using M = F approach. Sensitivity analyses will also be performed including an analysis excluding all missing data.

For the 3 key secondary safety endpoints (percentage change from baseline in hip BMD at Week 48, percentage change from baseline in spine BMD at Week 48, change from baseline in serum creatinine at Week 48), an analysis will be performed using the last observation carried forward (LOCF) method to impute missing data.

For the remaining endpoints, values for missing data will not be imputed, unless specified otherwise.

3.5.2. Outliers

Outliers may be identified during data management and data analysis process, but no sensitivity analyses will be done to evaluate the impact of outliers on efficacy or safety outcomes, unless specified otherwise. All data will be included in the analysis.

3.6. Data Handling Conventions and Transformations

Logarithm (base 10) will be used to transform HBV DNA and quantitative HBsAg data.

Data that are continuous in nature but are below the lower limit of quantitation or above the upper limit of quantitation will be imputed as follows except for direct bilirubin, urine creatinine, and serum cystatin C:

- A value that is 1 unit less than the limit of quantitation will be used for calculation of descriptive statistics if the datum is reported in the form of “< x” (x is considered as the limit of quantitation). For example, if the values are reported as < 50 and < 5.0, then values of 49 and 4.9 will be used for calculation of summary statistics, respectively.
- A value that is 1 unit above the limit of quantitation will be used for calculation of descriptive statistics if the datum is reported in the form of “> x” (x is considered as the limit of quantitation). Values with decimal points will follow the same logic as stated above.
- The limit of quantitation will be used for calculation of descriptive statistics if the data is reported in the form of “≤ x” or “≥ x” (x is considered as the limit of quantitation).

For direct bilirubin, a value of “< 0.1” is imputed as 0.09. For urine creatinine, a value of “< 1” is handled as a missing value in its summary and the calculation of related ratios. For serum cystatin C, a value of “< 0.10” is handled as a missing value in the calculation of estimated glomerular filtration rate (eGFR).

For HBV DNA, if the value in IU/mL (TaqMan) is above the upper limit of quantification, the corresponding diluted value (TaqDil), if available, will be used.

3.7. Analysis Windows

3.7.1. Definition of Study Day 1 and Other Definitions

Study Day 1 is defined as the day when the first dose of the blinded study drug was taken, as recorded on the Study Drug Administration eCRF form.

Open-Label Study Day 1 is defined as the day when the first dose of the open-label study drug was taken, as recorded on the Study Drug Administration eCRF form.

Study days are calculated relative to Study Day 1. For events that occurred on or after Study Day 1 date, study days are calculated as (visit date – Study Day 1 + 1). For events that occurred prior to Study Day 1, study days are calculated as (visit date – Study Day 1).

Open-Label Study days are calculated relative to Open-Label Study Day 1. For events that occurred on or after Open-Label Study Day 1 date, study days are calculated as (visit date – Open-Label Study Day 1 + 1).

Follow-up days are for visits occurred during 24-week treatment-free follow-up period and calculated as (visit date – last dose date).

Last Dose Date of Blinded Study Drug is the latest non-missing end date of blinded study drug, recorded on the Study Drug Administration eCRF form with “Study Drug Permanently Discontinued” box checked for subjects who prematurely discontinued blinded study drug or who completed blinded study drug according to Blinded Study Drug Completion eCRF. If the last dose date of blinded study drug is missing (eg, due to lost to follow up) for subjects who prematurely discontinued blinded study drug, or for subjects who are still on blinded study drug, the latest of nonmissing blinded study drug start dates and end dates, the clinical visit dates and the laboratory visit dates excluding the dates of open-label and 24-week treatment-free follow-up visits will be used to impute the last dose date of blinded study drug.

For subjects who prematurely discontinued blinded study drug or who completed blinded study drug but did not enter open-label phase, the **Last Dose Date** is the same as Last Dose Date of Blinded Study Drug.

For subjects who completed blinded study drug and entered open-label phase, the **Last Dose Date** is the latest non-missing end date of open-label study drug, recorded on the Study Drug Administration eCRF form with “Study Drug Permanently Discontinued” box checked for subjects who prematurely discontinued open-label study drug or who completed open-label study drug according to Open-Label Study Drug Completion eCRF. If the last dose date is missing (eg, due to lost to follow up) for subjects who prematurely discontinued open-label study drug, or for subjects who are still on open-label study drug, the latest of nonmissing open-label study drug start dates and end dates, the clinical visit dates and the laboratory visit dates excluding the dates of 24-week treatment-free follow-up visits will be used to impute the last dose date.

Last Study Date is the latest of nonmissing study drug (blinded or open-label) start dates and end dates, the clinic visit and the laboratory visit dates including the 24-week treatment-free follow-up visit date for subjects who prematurely discontinued study or who completed study according to Study Completion eCRF.

Baseline value is defined as the last nonmissing value obtained on or prior to Study Day 1. For DXA BMD, it is defined as the last value on or prior to Study Day 14.

3.7.2. Analysis Windows

Subject visits might not occur on protocol specified days. Therefore, for the purpose of analysis, observations will be assigned to analysis windows.

The following windows (Table 3-2 to Table 3-8) apply to baseline and on-treatment assessments only, ie, data collected up to the last dose date for those who discontinued study drug prematurely (except efficacy data [HBV DNA, quantitative HBsAg, HBV serology, ALT, fibrotest score] for subjects who discontinue study drug after Week 48 due to HBsAg loss with confirmed seroconversion to anti-HBs), or data collected up to database finalization date for those who have not discontinued study drug permanently.

For subjects who discontinue study drug early due to HBsAg loss with confirmed seroconversion, all efficacy data including data collected after the last dose date of the study drug will be reassigned analysis visits using the on-treatment assessment windows (Table 3-2, Table 3-3, and Table 3-5).

The analysis windows for HBV DNA, hematology, serum chemistry and liver function tests, urinalysis, urine pregnancy test, eGFR (by CG and Chronic Kidney Disease Epidemiology Collaboration [CKD-EPI]), renal biomarkers urine albumin to creatinine ratio (UACR), urine protein to creatinine ratio (UPCR), renal tubular maximum reabsorption rate of phosphate to the glomerular filtration rate (TmP/GFR), urine fractional excretion of filtered phosphate (FEPO₄), fractional excretion of uric acid (FEUA), weight, and vital sign assessments are presented in Table 3-2.

Table 3-2. Analysis Windows for HBV DNA, Hematology, Serum Chemistry and Liver Function Tests, Urinalysis, Urine Pregnancy Test, eGFR (by CG and CKD-EPI), PTH, UACR, UPCR, TmP/GFR, FEPO₄, FEUA, Weight, and Vital Sign Assessments

Visit ID	Nominal Day	Lower Limit	Upper Limit
Baseline			1
Week 4	28	2	41
Week 8	56	42	69
Week 12	84	70	97
Week 16	112	98	125
Week 20	140	126	153
Week 24	168	154	181
Week 28	196	182	209
Week 32	224	210	237
Week 36	252	238	265
Week 40	280	266	293
Week 44	308	294	321
Week 48	336	322	363
Week 56	392	364	419
Week 64	448	420	475
Week 72	504	476	531
Week 80	560	532	587
Week 88	616	588	643
Week 96	672	644	713
Week 108	756	714	797
Week 120	840	798	881
Week 132	924	882	965
Week 144	1008	966	1091
Week 168	1176	1092	1259
Week 192	1344	1260	1427
Week 216	1512	1428	1595
Week 240	1680	1596	1763
Week 264	1848	1764	1931
Week 288	2016	1932	2099
Week 312	2184	2100	2267
Week 336	2352	2268	2435
Week 360	2520	2436	2603
Week 384	2688	2604	2771

The analysis windows for safety ECG and fibrotest are presented in Table 3-3.

Table 3-3. Analysis Windows for Safety ECG and Fibrotest

Visit ID	Nominal Day	Lower Limit	Upper Limit
Baseline			1
Week 48	336	2	503
Week 96	672	504	839
Week 144	1008	840	1175
Week 192	1344	1176	1511
Week 240	1680	1512	1847
Week 288	2016	1848	2183
Week 336	2352	2184	2519
Week 384	2688	2520	2855

The analysis windows for BMD results from DXA, and fasting lipid panel including direct low density lipoprotein (LDL), high density lipoprotein (HDL) and total cholesterol to HDL ratio, are presented in Table 3-4.

Table 3-4. Analysis Windows for BMD Results from DXA and Fasting Lipid Panel

Visit ID	Nominal Day	Lower Limit	Upper Limit
Baseline			1(14 ^a)
Week 24	168	2(15a)	251
Week 48	336	252	419
Week 72	504	420	587
Week 96	672	588	839 (755 ^b)
Week 120 ^b	840	756b	923b
Week 144	1008	840 (924 ^b)	1175
Week 192	1344	1176	1511
Week 240	1680	1512	1847
Week 288	2016	1848	2183
Week 336	2352	2184	2519
Week 384	2688	2520	2855

a This applies to DXA only. Upper limit for baseline DXA BMD is Day 14 and lower limit for Week 24 DXA BMD is Day 15.

b This applies to the subjects who consented to Amendment 3.1.

The analysis windows for serum HBsAg (quantitative) and HBV serology are presented in Table 3-5.

Table 3-5. Analysis Windows for Serum HBsAg (Quantitative) and HBV Serology

Visit ID	Nominal Day	Lower Limit	Upper Limit
Baseline			1
Week 12	84	2	125
Week 24	168	126	209
Week 36	252	210	293
Week 48	336	294	391
Week 64	448	392	503
Week 80	560	504	615
Week 96	672	616	713
Week 108	756	714	797
Week 120	840	798	881
Week 132	924	882	965
Week 144	1008	966	1091
Week 168	1176	1092	1259
Week 192	1344	1260	1427
Week 216	1512	1428	1595
Week 240	1680	1596	1763
Week 264	1848	1764	1931
Week 288	2016	1932	2099
Week 312	2184	2100	2267
Week 336	2352	2268	2435
Week 360	2520	2436	2603
Week 384	2688	2604	2771

The analysis windows for fasting glucose, fasting total cholesterol, fasting triglycerides, renal biomarkers including urine retinol binding protein (RBP) to creatinine ratio, urine beta-2-microglobulin to creatinine ratio, and bone biomarkers including C-type collagen sequence (CTX), procollagen type 1 N-terminal propeptide (P1NP), osteocalcin (OC), and bone specific alkaline phosphatase (bsAP) are presented in Table 3-6.

Table 3-6. Analysis Windows for Fasting Glucose, Fasting Total Cholesterol, Fasting Triglycerides, Renal, and Bone Biomarkers

Visit ID	Nominal Day	Lower Limit	Upper Limit
Baseline			1
Week 4	28	2	55
Week 12	84	56	125
Week 24	168	126	251
Week 48	336	252	419
Week 72	504	420	587
Week 96	672	588	839 (755 ^a)
Week 120 ^a	840	756 ^a	923 ^a
Week 144	1008	840 (924 ^a)	1175
Week 192	1344	1176	1511
Week 240	1680	1512	1847
Week 288	2016	1848	2183
Week 336	2352	2184	2519
Week 384	2688	2520	2855

a This applies to the subjects who consented to Amendment 3.1

The analysis window for serum parathyroid hormone (PTH) is presented in Table 3-7.

Table 3-7. Analysis Windows for PTH

Visit ID	Nominal Day	Lower Limit	Upper Limit
Baseline			1
Week 4	28	2	41
Week 8	56	42	69
Week 12	84	70	97
Week 16	112	98	125
Week 20	140	126	153
Week 24	168	154	181
Week 28	196	182	209
Week 32	224	210	237
Week 36	252	238	265
Week 40	280	266	293
Week 44	308	294	321
Week 48	336	322	363
Week 56	392	364	419
Week 64	448	420	475
Week 72	504	476	531
Week 80	560	532	587
Week 88	616	588	643
Week 96	672	644	713
Week 108	756	714	797
Week 120	840	798	881
Week 132	924	882	965
Week 144	1008	966	1175
Week 192	1344	1176	1511
Week 240	1680	1512	1847
Week 288	2016	1848	2183
Week 336	2352	2184	2519
Week 384	2688	2520	2855

The analysis window for hepatic ultrasound for hepatocellular carcinoma (HCC) surveillance is presented in Table 3-8.

Table 3-8. Analysis Windows for Hepatic Ultrasound

Visit ID	Nominal Day	Lower Limit	Upper Limit
Baseline			1
Week 96	672	588	755
Week 120	840	756	923
Week 144	1008	924	1091
Week 168	1176	1092	1259
Week 192	1344	1260	1427
Week 216	1512	1428	1595
Week 240	1680	1596	1763
Week 264	1848	1764	1931
Week 288	2016	1932	2099
Week 312	2184	2100	2267
Week 336	2352	2268	2435
Week 360	2520	2436	2603
Week 384	2688	2604	2855

This applies to the subjects who consented to Amendment 3.1.

Data collected after the last dose date will be considered as post-treatment visits. The analysis windows for post-treatment assessments are presented in Table 3-9 and Table 3-10.

Table 3-9. Analysis Windows for Post-Treatment Assessments except HBV Serology

Visit ID	Nominal Follow-Up Day	Lower Limit	Upper Limit
Follow-Up Week 4	28	1	41
Follow-Up Week 8	56	42	69
Follow-Up Week 12	84	70	97
Follow-Up Week 16	112	98	125
Follow-Up Week 20	140	126	153
Follow-Up Week 24	168	154	181

Table 3-10. Analysis Windows for Post-Treatment HBV Serology

Visit ID	Nominal Follow-Up Day	Lower Limit	Upper Limit
Follow-Up Week 12	84	1	125
Follow-Up Week 24	168	126	209

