Subjects Experiencing Any Grade 3 or 4 Treatment-Emergent Adverse Event	8 (7.1%)	2 (3.4%)
Subjects Experiencing Any Treatment-Emergent Study-Drug-Related Adverse Event	38 (33.9%)	15 (25.9%)
Subjects Experiencing Any Grade 2, 3, or 4 Treatment-Emergent Study-Drug-Related Adverse Event	6 (5.4%)	1 (1.7%)
Subjects Experiencing Any Grade 3 or 4 Treatment-Emergent Study-Drug-Related Adverse Event	1 (0.9%)	0
Subjects Experiencing Any Treatment-Emergent Serious Adverse Event	6 (5.4%)	2 (3.4%)
Subjects Experiencing Any Treatment-Emergent Study-Drug-Related Serious Adverse Event	0	0
Subjects Experiencing Any Treatment-Emergent Adverse Event Leading to Premature Study Drug Discontinuation	4 (3.6%)	0
Subjects who had Treatment-Emergent Death	0	0

Treatment-emergent death refers to a death occurring between the first dose date and the last dose date plus 30 days (inclusive).

At least 1 treatment-emergent laboratory abnormality (ie, at least 1 grade level increase in graded abnormality) was reported for 103/111 subjects (92.8%) in the E/C/F/TAF group and 46/58 subjects (79.3%) in the E/C/F/TDF group. The majority of laboratory abnormalities were Grade 1 or 2 in severity. Subject incidence of Grade 3 or 4 treatment-emergent laboratory abnormalities is summarized in [Table 1-8](#).

Table 1-8. GS-US-292-0102: Treatment-Emergent Grade 3 or 4 Laboratory Abnormalities, Safety Analysis Set

	E/C/F/TAF (N = 112)	E/C/F/TDF (N = 58)
Maximum Post-Baseline Toxicity Grade 3 or 4	19 (17.1%)	8 (13.8%)
Neutrophils	5 (4.5%)	1 (1.7%)
WBC	1 (0.9%)	0
Amylase	2 (1.8%)	1 (1.7%)
Creatine Kinase (CK)	6 (5.4%)	2 (3.4%)
Lipase	0	1 (12.5%)
Serum Glucose (Hyperglycemia)	0	1 (1.7%)
Total Cholesterol (Fasting, Hypercholesterolemia)	1 (0.9%)	0
Triglycerides (Fasting)	1 (0.9%)	1 (1.7%)
LDL (Fasting)	7 (6.4%)	2 (3.4%)
Urine Protein (Proteinuria)	1 (0.9%)	0
Urine RBC (Hematuria, Quantitative)	1 (0.9%)	0

Denominator for percentage is the number of subjects in the SAS with at least 1 post-baseline laboratory value (for the test).

Subjects were counted once for the maximum postbaseline severity for each laboratory test.

Lipase test was only performed for subjects with serum amylase $> 1.5 \times$ upper limit of normal.

Urine RBC (hematuria, quantitative) was graded based on DAIDS grading scale (with the modification of urine RBC > 75 cells/HPF as Grade 3).

For Urinalysis (i.e., urine glucose, urine protein, and urine RBC), the highest grade is up to Grade 3.

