6.3.2.2. Weeks 192, 240, 288, 336, and 384/ED

The ED Visit should be performed within 72 hours (i.e., visit window is within 3 days) of the last study drug dose.

- Symptom directed physical exam (**At Week 240 and 384/ED**, a complete physical exam should be performed)
- Hepatic ultrasound for surveillance of hepatocellular carcinoma

At ED visit, Hepatic ultrasound should be performed only if not done within the prior 24 weeks

- Body weight
- Vital signs: blood pressure, pulse, respiration rate, and temperature
- ECG (subjects must rest quietly in the supine position for a minimum of 5 minutes prior to the recording)
- DXA scan of spine and hip to be performed (within ± 28 days of the expected visit date; at sites in China with DXA capability only)

At ED visit, DXA scan should be performed only if not done within the prior 24 weeks

- Review concomitant medications
- Review adverse events
- Retrieve study drug and perform study drug accountability
- Dispense Open Label TAF (no study drug will be dispensed at Week 384/ ED visit)

- Fasting blood sample for bone biomarkers and metabolic assessment (glucose and lipid panel [total cholesterol, HDL, direct LDL, and triglycerides]) - no food or drinks, except water, at least 8 hours prior to blood collection
- Fasting urine sample for renal biomarkers
- Blood sample for serum chemistry and liver function tests, hematology, plasma HBV DNA, serum HBsAg (quantitative), HBV serology (HBsAb and reflex HBsAg), virology (resistance surveillance), and serum and plasma for storage
- Estimated creatinine clearance (using the Cockcroft-Gault method)
- Blood sample for Fibrotest[®]
- Urine sample for urinalysis, pregnancy test (for females of child-bearing potential; in case of a positive urine test, a serum pregnancy test will be done), and for storage
- **For ED visit prior to Week 144 only, if not performed within the prior 24 weeks:**
Ophthalmologic assessment, including fundoscopic examination with slit lamp and retinal photographs (both eyes) (**substudy subjects only at select sites** - separate consent required)

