- n For a subset of subjects (n = 30), who provide a separate consent form, a substudy will be conducted to assess ophthalmologic findings, including fundoscopic examination with retinal photographs (both eyes). The examination can be conducted anytime during the screening period, but must be completed prior to the first dose of the study drug, and will be conducted at Weeks 24, 48, 72, 96, and 144 at select sites. Required for Early Discontinuation (ED) visit if prior to Week 144 and not done within the last 24 weeks. An examination of the full retinal field should be conducted noting changes or abnormalities. Photographs of the retina must be taken at each exam and filed in the subject's source medical records. A central vendor will be used to assess the retinal photographs.
- o The Early Discontinuation (ED) visit should be performed within 72 hours of the last study drug dose (+ 3 days)
- p Subjects who discontinue study drug for reasons other than HBsAg loss with confirmed seroconversion to anti-HBs will be followed every 4 weeks for 24 weeks or up to initiation of alternative, commercially available HBV therapy, whichever occurs first. Subjects who lose HBsAg with confirmed seroconversion to anti-HBs should discontinue study drug within 3-6 months following confirmation of HBsAg loss and seroconversion to anti-HBs or after Week 48, if seroconversion occurs prior to this visit. These subjects will be followed off treatment every 4 weeks for 12 weeks and then per the study visit schedule through Week 384/ED.
- q Complete the Fracture Risk Assessment specific eCRF at sites in China with DXA capability only.
- r Hepatic ultrasound for HCC surveillance

Appendix 3. Intensive Pharmacokinetic Substudy Assessment Schedule (at selected sites in a subset of subjects [n=16 and up to n=32])

Time Point (Once at either of the Week 4, 8 or 12 visits)
0 (within 30 minutes of dose)*
5 minutes post dose
15 minutes post dose
30 minutes post dose
45 minutes post dose
1 hour post dose
1.5 hours post dose
2 hours post dose
3 hours post dose
4 hours post dose
5 hours post dose
8 hours post dose
12 hours post dose
24 hours post dose

* Subjects participating in the PK substudy (at sites which can process PBMCs), will also be asked to provide a PBMC (pre-dose) sample at the intensive PK substudy visit to assess intracellular TFV-DP concentration in PBMCs

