7. SAFETY ANALYSES

For Week 48 analysis, safety data will be summarized for the double-blind phase only up to Week 96. The upper limit of the least frequent schedule analysis window of Week 96 (Study Day 839) will be used as Week 96 data cut for cumulative summaries of safety events (eg, treatment-emergent AEs, treatment-emergent laboratory abnormalities). All safety data up to the Week 48 data-cut including data collected during the open-label phase and the 24-week treatment-free follow-up period will be included in data listings.

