7.1.7. Summaries of AEs and Deaths

A brief summary of AEs (ie, the number and percentage of subjects) will be presented by treatment group for the following: (1) any treatment-emergent AE, (2) any Grade 3 or 4 treatment-emergent AE, (3) any Grade 2, 3 or 4 treatment-emergent AE, (4) any treatment-emergent study drug-related AE, (5) any Grade 3 or 4 treatment-emergent study drug-related AE, (6) any Grade 2, 3 or 4 treatment-emergent study drug-related AE, (7) any treatment-emergent serious adverse event (SAE), (8) any treatment-emergent study drug-related SAE,

- (9) any treatment-emergent AE leading to premature study drug discontinuation,
- (10) any treatment-emergent AE leading to dose modification or study drug interruption, and
- (11) any treatment-emergent death.

Treatment-emergent death refers to death that occurs between the first dose date and the last dose date (inclusive).

Summaries (number and percentage of subjects) of AEs (by SOC, HLT [if specified below], and PT) will be provided by treatment group and overall using the Safety Analysis Set as follows:

- All treatment-emergent AEs summarized by SOC, HLT, and PT
- Any Grade 3 or 4 treatment-emergent AEs
- Any Grade 2, 3, or 4 treatment-emergent AEs
- All treatment-emergent nonserious AEs occurring in at least 5% of subjects in any treatment group (this summary is generated per requirement for reporting in ClinicalTrials.gov)
- All treatment-emergent study drug-related AE summarized by SOC, HLT, and PT
- Any Grade 3 or 4 treatment-emergent study drug-related AEs
- Any Grade 2, 3, or 4 treatment-emergent study drug-related AEs
- All treatment-emergent SAEs
- All treatment-emergent study drug-related SAEs
- All treatment-emergent AEs leading to premature discontinuation from study drug
- All treatment-emergent AEs leading to dose modification or study drug interruption

Multiple events will be counted once only per subject in each summary. For data presentation, SOC (and HLT) will be ordered alphabetically, with PT sorted by decreasing total frequency. For summaries by severity grade, the most severe event will be selected.

In addition to the by-treatment summaries, data listings will be provided for the following:

- All AEs
- Grade 3 and 4 AEs
- SAEs

- Study drug-related SAEs
- Deaths
- AEs leading to premature discontinuation of study drug
- AEs leading to dose modification or study drug interruption

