7.2.2.1. Treatment-Emergent Laboratory Abnormalities

Treatment-emergent laboratory abnormalities occurring in the double-blind phase are defined as values that increase by at least 1 toxicity grade from baseline at any postbaseline visit up to and including the last dose date of the blinded study drug (or 'last dose date of the blinded study drug + 1' for those who enter the open-label phase) for those who discontinued blinded study drug prematurely, or values that increase by at least 1 toxicity grade from baseline at any postbaseline visit for those who are still on the blinded study drug. If the relevant baseline laboratory data are missing, any laboratory abnormality of at least Grade 1 will be considered treatment-emergent.

Treatment-emergent laboratory abnormalities occurring in the open-label phase are defined as values that increase by at least 1 toxicity grade from the open-label baseline at any open-label postbaseline visit up to and including the last dose date of open-label study drug for those who discontinued open-label study drug prematurely, or values that increase by at least 1 toxicity grade from the open-label baseline at any open-label postbaseline visit for those who are still on the open-label study drug. For the analyses of abnormalities occurring during open-label treatment, baseline will be considered to be the last available record on or prior to Open-Label Study Day 1.

Fasting glucose and nonfasting glucose are graded based on different grading scales. Treatment-emergent laboratory abnormalities will be summarized for fasting glucose. Since nonfasting glucose was not assessed at baseline, the maximum postbaseline grade will be summarized.

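### Early-discontinuation results taken 1 to 3 days after the last dose are coded as follow-up, so they miss the on-treatment safety summaries and the LOCF

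*SAP*

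**What the plan says.** **Cut-off.** For premature discontinuers, SAP 3.7.2 restricts the baseline and on-treatment windows to "data collected up to the last dose date for those who discontinued study drug prematurely". Beyond that date, "Data collected after the last dose date will be considered as post-treatment visits". Follow-Up Week 4 covers follow-up Days 1 to 41 (Table 3-9). For HBV serology the first follow-up window is Days 1 to 125 (Table 3-10).

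**ED visit.** Protocol 6.3.2.2 states: "The ED Visit should be performed within 72 hours (i.e., visit window is within 3 days) of the last study drug dose". A footnote to the procedures table in Appendix 2 gives the same 3-day allowance after the dose.

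**Use of the data.**
- SAP 7 states that "safety data will be summarized for the double-blind phase only up to Week 96". Data from treatment-free follow-up go to listings, and SAP Appendix 1 contains no summary table for that period.
- Treatment-emergent laboratory abnormalities in premature discontinuers are judged at "any postbaseline visit up to and including the last dose date of the blinded study drug" (SAP 7.2.2.1).
- LOCF for BMD (SAP 7.3.1) and serum creatinine (SAP 7.4.2) draws only on postbaseline values obtained on treatment, and baseline is not carried forward.
- SAP 7.1.7 ends its count of treatment-emergent deaths on the last dose date.

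**Protocol rule.** Protocol 8.6 also summarizes safety data only to the last dose and lists the follow-up period. Sections 8.6.3 and 8.6.4 end treatment-emergence for AEs and laboratory values at the same point. Protocol 7.3 nevertheless collects all AEs for 4 weeks after the last dose.

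**The concern.** The ED visit is the assessment meant to record a subject's condition on leaving study drug. Under the SAP's date rule, one held on the day of the last dose is on-treatment, while one held the next day, still fully on schedule, is not. Subjects who stop for renal, hepatic or bone reasons are those whose final creatinine, ALT, urinalysis or DXA is most informative.

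If the ED value is reclassified, the creatinine LOCF uses an older value. A subject whose ED scan is the only postbaseline DXA contributes nothing to the BMD LOCF. An abnormality first seen at that visit does not reach the treatment-emergent tables. Hip BMD, spine BMD and serum creatinine are the protocol's key secondary safety endpoints, and the China TDF arm has only about 50 subjects.

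**Working it through.** The plan states no figure on this point, so there is none to reproduce. The check uses the date rules, followed by a size estimate under stated assumptions.

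**Step 1: where an ED visit falls.** Follow-up day = visit date − last dose date (SAP 3.7.1).

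| ED lag after last dose | Follow-up day | Classification |
|---|---|---|
| 0 days | none | On-treatment |
| 1, 2 or 3 days | 1, 2 or 3 | Follow-Up Week 4 (Follow-Up Week 12 for serology) |

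All four lags comply with the protocol, but only the first counts as on-treatment.

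**Step 2: does the SAP treat a short lag consistently?**
- If the last dose date is missing, SAP 3.7.1 imputes it from the latest visit or laboratory date, leaving out only open-label and follow-up visits. The same ED visit would then be on-treatment, so its classification depends on whether a date was recorded.
- SAP 3.7.1 accepts a DXA up to Study Day 14 as baseline. On that logic, a lag of 1 to 3 days is immaterial for BMD.

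**Step 3: size.** The documents give no discontinuation rate for the China cohort. Assume 5 to 10% of 150 by Week 48, spread evenly over 336 days: 150 × 0.05 = 7.5 and 150 × 0.10 = 15 discontinuers.

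*Safety labs.* Every discontinuer with an ED lag of 1 to 3 days is exposed, so at most about 8 to 15 subjects. The lag distribution is unknown. One event is 1/50 = 2 percentage points in the TDF arm and 1/100 = 1 point in the TAF arm.

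*Week 48 HBV DNA.* The window is Days 322 to 363 (SAP Table 3-2).
- With a lag of up to 3 days, the earliest relevant last-dose day is 322 − 3 = 319.
- The last such day before nominal Day 336 is 335, which gives 335 − 319 + 1 = 17 days.
- 17/336 = 5.1%. Then 7.5 × 17/336 = 0.38 and 15 × 17/336 = 0.76, or about 0.4 to 0.8 subjects.

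*DXA.* The ED scan is done only if there was none in the prior 24 weeks (168 days; protocol 6.3.2.2).
- The baseline scan can be up to 45 days before dosing, so an ED scan can fall due from about Day 168 − 45 + 1 = 124.
- The Week 24 scan is due by Day 168 + 14 = 182, which gives at most 182 − 124 + 1 = 59 days.
- 7.5 × 59/336 = 1.32 and 15 × 59/336 = 2.63, so at most about 1.3 to 2.6 subjects for whom the ED scan is the only postbaseline scan.
- This is an upper bound. It takes the earliest possible baseline scan and assumes all 150 are scanned, although only DXA-capable sites do so.

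**Step 4: would Day 4 displace a real follow-up visit?** The first is due at Day 28 ± 7 (protocol 6.4.3), so Day 21 at the earliest. A lower limit of Day 4 displaces none.

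**The case against.** The best defence is that the SAP applies the protocol's own rule. A reader might infer a conflict between SAP and protocol, but protocol 8.6, 8.6.3 and 8.6.4 all stop at the last dose. This stands: the weakness belongs to both documents, and changing it is a departure that must be declared.

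A reader might also infer that the data are lost or that harm is hidden. The documents do not support that:
- The values remain in listings. SAP 7.2.3 lists ALT elevations that are not treatment-emergent, SAP 7.4.1 lists confirmed renal abnormalities arising in follow-up, and deaths have their own listing (Listing 26).
- An AE leading to discontinuation is treatment-emergent whatever its onset date (SAP 7.1.6.1), and a laboratory abnormality that leads to discontinuation must be recorded as an AE (protocol 7.1.3).
- Protocol 7.5 asks for clinically significant Grade 3 and 4 values to be confirmed before stopping, unless delay is inconsistent with good practice. The triggering value is therefore usually on-treatment.
- Chemistry is scheduled every 4 weeks to Week 48, so the creatinine LOCF usually has a value from the preceding month.

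A third tempting reading is that open-label entrants are favoured, since they receive 1 extra day for labs and until open-label Day 14 for DXA. Per SAP 1.2, all China subjects complete 3 years of blinded treatment first, and these summaries stop at Week 96, so the allowances should not affect this analysis.

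Finally, a reader might take last dose + 30 days as the established rule for deaths. In these documents it appears only in a table footnote for another study, the HIV Phase 2 trial (protocol Table 1-7). A fatal event with onset by the last dose is still a treatment-emergent SAE here.

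What remains is the classification of on-schedule ED results in the summary tables and the LOCF. None of these safeguards restores them there.

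**Conclusion.** The point holds as a limited one. An ED visit 1 to 3 days after the last dose complies with the protocol, yet its results are excluded from the treatment-emergent laboratory, ALT, proteinuria and renal summaries and from the creatinine and BMD LOCF. ED visits on the last-dose date are unaffected, as are those where the last-dose date is missing and imputed.

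Safety labs at discontinuation carry most of the effect, for up to about 8 to 15 subjects. The figures rest on an assumed 5 to 10% discontinuation rate, even timing over 336 days and, for labs, ED visits that all fall after the last-dose date.

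A reader might infer that the primary endpoint is materially affected. It is not: well under one Week 48 HBV DNA value would be expected to change status at 5%, and fewer than one at 10%, because most earlier discontinuers are failures under missing = failure anyway. The change is worth making because it is cheap and recovers safety data at the point of discontinuation, not because the current rule invalidates any result.

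**What to change.** - In SAP 3.7.2, 7.2.2, 7.3.1 and 7.4.2, treat ED-visit assessments up to the last dose date + 3 days as on-treatment for premature discontinuers.
- Start the first follow-up window in Tables 3-9 and 3-10 on Day 4.
- Declare the departure from protocol 8.6 in SAP 7.11.
- Leave the definition of treatment-emergent death in SAP 7.1.7 unchanged, and add a summary row for deaths within the 4-week post-dose AE collection period of protocol 7.3.

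The cost is SAP wording, derivation flags and one table row, with no new data collection. As a downside, a few values obtained 1 to 3 days off drug would count as on-treatment. The tables may also differ slightly from the completed non-China Week 48 analysis, which matters because protocol 8.5.2 uses the China analysis to examine consistency with the overall population. The entry in SAP 7.11 should say so.
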